5.3.4. Assessment of symptoms

To reduce bias, assessment of symptoms will be performed by the subject, using the OSDI questionnaire, *before* any ocular examination or assessment of study outcome is performed by the examiner. In addition, the subject will also self-assess his/her symptoms using the EDS score with a VAS. The changes of OSDI and EDS, from baseline to the follow-up, will be used to estimate the secondary endpoints.

5.3.5. Assessment of TBUT

TBUT will be measured for each eye separately as follows:

- A FUL-GLO[®] fluorescein sodium ophthalmic strip (0.6 mg) will be applied to the inferior tarsal conjunctiva
- The subject will be asked to blink a few times to distribute the dye over the ocular surface.
- Once positioned at the slit lamp, the subject will close his/her eye completely.
- Then, the subject will be asked to open his/her eye without blinking.
- The timer will start as soon as the subject opens his/her eye, and it will be stopped at the first sign of tear film break of dry spot formation (first dark spot or discontinuity in the precorneal fluorescein-stained tear layer).
- For each eye, 3 consecutive readings will be taken
- TBUT will be calculated as the average of these 3 readings.

The *change* of TBUT, from baseline to the follow-up, will be used as the primary efficiency endpoint.

QF-1044440 Rev. D Glo	obal Clinical Study Report Template	GEN-0010523	Effective Date: July-2017
-----------------------	-------------------------------------	-------------	---------------------------

Revision: C State: Released ECO No: ca-00000172 Effective Date: 19-Sep-2019

5.3.6. Routine ophthalmic examinations

Routine ophthalmic examinations, performed separately for each eye, will include: biomicroscopy with the slit lamp (consisting of observation of the lid margins, conjunctiva, and eye lashes), BCVA with an ETDRS chart, and IOP with tonometry.

5.3.7.Close-up photos of the eyes

Close-up photos of both eyes will be captured with a high-resolution camera (> 325 ppi). Image resolution should be high enough to see the lid margins, the iris and individual eye lashes in focus.

For best results, the camera should be used in "Macro" mode. For a simpler camera with no macro mode (for example. iPhone 7), position the camera at a distance of 30-40 cm from the eye, and use the optic zoom to take a close-up photo. If a mobile phone camera is used, it is advised to use a second mobile phone to provide illumination, rather than rely on the flash capabilities of the camera (for an example, see **Error! Reference source not found.**).

5.3.8. Meibography

Meibography of the upper and lower eyelids in both eyes will be performed using an ophthalmic imaging device with a built-in infra-red camera, such as Lipiscan/Lipiview (TearScience/Johnson & Johnson), Keratograph 5M (Oculus), Antares (CSO/Lumenis) or equivalent system. While the patient rests his/her head on the chin rest, the eyelid will be gently everted (turned over) using a cotton tip applicator, and an image of the eyelid will be captured.

The percentage of area loss of the meibomian glands will be evaluated using a 5-point scale, as illustrated in Figure 8: 0: no loss; 1: < 25 % loss; 2: 26%-50\% loss; 3: 51%-75\% loss; 4: > 75% loss.

5.3.9.MGS score

The MGS score will be estimated for each eye separately as described by Lane and colleagues [29]:

- Along the lower eyelid, 15 glands will be evaluated: 5 nasal, 5 central and 5 temporal.
- Each group of 5 glands will be squeezed with Q-tips or with the Cunningham expressor (Storez) for 8 seconds or until all 5 glands are expressed, which ever comes first.
- Each gland will be graded as follows: 3 = clear liquid secretion, 2 = cloudy liquid secretion; 1 = inspissated/toothpaste consistency; 0 = no secretion.
- MGS will be estimated as the sum of grades of these 15 glands (range: 0 to 45).

QF-1044440 Rev. D	Global Clinical Study Report Template	GEN-0010523	Effective Date: July-2017

Revision: C State: Released ECO No: ca-00000172 Effective Date: 19-Sep-2019

5.4. Termination visit

Normally, termination should occur at the follow-up visit after all tests were performed. In case the subject shows excessive immediate skin reaction after several test spots, early termination can occur at any of the treatment visits. The reason for early termination should be documented in the termination eCRF. The Study Exit/Termination eCRF should be signed with the study investigator's signature.

6. Study Evaluations

6.1. Efficiency

6.1.1. Primary effectiveness endpoint

The primary efficiency endpoint will be estimated as the difference in the *change* of TBUT from baseline to follow-up (10 weeks) between the study arm and the control arm, where the change of TBUT is defined as TBUT at the follow-up minus TBUT at the baseline.

A linear mixed-effect (LME) model will be used to test the null hypothesis that the changes of TBUT are not different between the two arms. The success criterion will include the following two conditions:

- 1. Two-sided p-value < 0.05
- 2. The change of TBUT in eyes of the study arm is *larger* than the change of TBUT in eyes of the control arm

The linear mixed-effect model will include a random effect for subjects to account for correlation between eyes within subjects.

6.1.2. Secondary effectiveness endpoints

The following secondary efficiency endpoints will be estimated:

- The difference in the *change* of EDS, between subjects in the study arm and subjects in the control arm
- The difference in the *change* of OSDI, between subjects in the study arm and subjects in the control arm

, where *change* is defined as the value of the variable (OSDI or EDS) at the follow-up minus the value of the variable at the baseline.

Revision: C State: Released ECO No: ca-00000172 Effective Date: 19-Sep-2019

6.1.3. Exploratory effectiveness endpoints

The following exploratory endpoints will be evaluated:

- The difference in the proportions of subjects with TBUT > 10 sec at the follow-up, between eyes in the study arm and eyes in the control arm
- The difference in the proportions of subjects with OSDI < 23 at the follow-up, between subjects in the study arm and subjects in the control arm
- The difference in eyelids appearance at the follow-up, as qualitatively evaluated by the study investigator, between eyes in the study arm and eyes in the control arm
- The difference in the percentage of area loss of meibomian glands, as evaluated using meibography, between eyes in the study arm and eyes in the control arm
- The difference in the change of MGS from BL to FU, between eyes in the study arm and eyes in the control arm

, where the *change* of a variable is defined as the value of this variable at the follow-up minus its value at the baseline.

6.2. Safety

Safety will be assessed by reporting:

- The difference in the incidence of related adverse events, between subjects in the treatment arm and subjects in the control arm
- The difference in the incidence of unrelated adverse events, between subjects in the treatment arm and subjects in the control arm
- The difference in the level of pain/discomfort during IPL treatment, between subjects in the treatment arm and subjects in the control arm
- The difference in the level of pain/discomfort during MGX, between subjects in the treatment arm and subjects in the control arm

7. Study Analysis Plan

7.1. Primary Study Hypothesis

The *change* of TBUT (Δ TBUT) in eyes of the study arm is *more positive* than Δ TBUT in eyes of the control arm,

, where \triangle TBUT is defined as TBUT at the follow-up minus TBUT at the baseline, and subscripts S, C indicate the study (S) or control (C) arms:

H0: $\Delta TBUT_{S} \leq \Delta TBUT_{C}$

H1: $\Delta TBUT_{S} > \Delta TBUT_{C}$

7.2. Secondary Study Hypotheses

1. The change of OSDI (\triangle OSDI) in subjects of the study arm is *more negative* than \triangle OSDI in subjects of the control arm,

, where $\triangle OSDI$ is defined as OSDI at the follow-up minus OSDI at the baseline:

H0: $\triangle OSDI_S \ge \triangle OSDI_C$ H1: $\triangle OSDI_S < \triangle OSDI_C$

2. The change of EDS (\triangle EDS) in subjects of the study arm is *more negative* than \triangle EDS in subjects of the control arm,

, where ${\scriptstyle\Delta}\text{EDS}$ is defined as EDS at the follow-up minus EDS at the baseline:

H0: $\triangle EDS_{s} \ge \triangle EDS_{c}$ H1: $\triangle EDS_{s} < \triangle EDS_{c}$

7.3. Sample Size

Approximately 4 months after initiation of the study, a round of site monitoring visits revealed that one of the three sites in the study was not following the instructions above with respect to where the M22 IPL lightguide should be applied; for IPL and sham subjects the lightguide was being applied too far from the eyelid margin in contrast to what is described in Figure 5 above. As a result, it is possible that the IPL treatments among the initial cohort of subjects at that site was will prove to be ineffective, or of reduced effectiveness compared to the sham control. The lightguide was applied correctly at the other two sites.

QF-1044440 Rev. D Global Clinical Study Report Template GEN-0010523 Effective Date: July-2017	

Although no data were unmasked, soon after this issue was recognized by study monitors, Lumenis initiated a corrective action (retraining and greater emphasis in the protocol), to better assure the protocol instructions would be followed.

To restore the original statistical power, the sample size was increased. Below are the original and adjusted calculations of the sample size:

7.3.1. Original calculation of the sample size

Assuming a 1:1 randomization ratio, a mean of 5 ± 5 sec for \triangle TBUT of the study arm, a mean of 1 ± 5 sec for \triangle TBUT of the control arm, an alpha level of 0.05 and a power of 80%, the total sample size is 50 completed study eyes (25 for the study arm and 25 for the control arm). Assuming a dropout rate of 15%, the anticipated number of enrolled subjects is 58. Assuming a screening failure rate of 15%, the anticipated total number of screened subjects is 66.

In addition, MGD is less common without concomitant skin rosacea. Therefore, enrollment will continue until at least 10 subjects without skin rosacea are enrolled, even if 58 subjects were already enrolled.

7.3.2. Adjusted calculation of the sample size.

After the corrective action to remedy the treatment errors, the sample size was recalculated using a simulation where we made the following conservative assumptions:

- The initial 8 IPL subjects at the affected site had response equal to the control arm (1±5 seconds)
- Subsequent to the corrective action, IPL subjects at the affected site had a response equal to the IPL arm (5±5 seconds)
- The final analysis was ITT, which included the inappropriately treated patients in the IPL arm.
- The correlation between eyes within a subject is 0.5.

Under these assumptions the overall treatment effect is "diluted" by the initial set of patients who were treated inappropriately. Under these conservative assumptions, the sample size needed to restore the original power was calculated to be 136 evaluable eyes (68 subjects, i.e. 18 subjects more than the original 50 subjects).

In addition, in order to allow for full comparison of the effect of the corrective action, 15 patients were added to the enrollment at the affected site so there would be sufficient before/after patients to allow for clinical evaluation of the difference.

QF-1044440 Rev. D Global Clinical Study Report Template GEN-0010523 Effective Date: July-201	-2017
--	-------

Adding these 33 (18+15) subjects to the original 50 completed subjects, the number of completed subjects is up to 83. Therefore, with a loss to follow-up rate of 7% the expected number of enrolled subjects is 89, and with a screening failure rate of 23% the expected number of screened subjects is 116.

All sample size re-calculations were done prior to any unmasking of any results from the study.

7.4. Study analyses

The primary efficacy outcome measure (TBUT) consist of a pre-treatment measurement (the baseline), a treatment intervention, and a post-treatment measurement (the follow-up). Both eyes will be included in the analysis. Since the two eyes of a subject are not independent, to estimate whether TBUT has improved from the baseline to the follow-up, a linear mixed effects model with random intercept, using the subject identity as the random effect, is the appropriate test. Since there are two eyes per person then there is only one possible covariance structure (i.e. symmetric, with a single correlation between eyes).

The secondary efficacy outcome measures are OSDI and EDS which will be collected at the baseline, and at a follow-up visit. In the case of OSDI, the value is estimated per subject. Hence, a single value will be collected per subject at each of these two visits. In this case a paired t-test is the appropriate statistical test to estimate whether dry eye symptoms have improved, using the change of OSDI from baseline to the follow-up. In the case of EDS, the value is estimated per eye. Hence, two values will be collected per subject at each of these two visits. Since the two eyes of a subject are not independent, to estimate whether EDS has improved from the baseline to the follow-up, a linear mixed effects model with random intercept, using the subject identity as the random effect, is the appropriate test. The level of statistical significance is $\alpha = 0.05$. Non-parametric tests will be performed if the underlying distributions are not normal.

For all other eye-level analyses, where appropriate, sample means of continuous variables will be analyzed with linear mixed effects model with random intercept (whenever both eyes of a subject are included in the analysis), or two-sample t-tests. Proportions will be analyzed with χ^2 tests.

All statistical tests will be two-sided because potentially the treatment procedure may worsen the outcome. The level of statistical significance (type I error) is $\alpha = 0.05$. Non-parametric tests will be performed if the underlying distribution is not normal.

For descriptive statistics, the N, Mean, Median, Standard deviation, Standard error of the mean, 95% confidence interval, Minimum, and Maximum will be reported for continuous variables; the frequency and proportion for each category will be reported for nominal and categorical variables.

A previous study demonstrated that in subjects with a lower TBUT at the baseline, the change in TBUT at the follow-up was larger [21]. Although not shown in this study, the severity level of skin rosacea at the baseline may also be a confounder. Hence, in addition to the primary analysis, we will carry out an analysis of covariance (ANCOVA) to adjust for these covariates.

QF-1044440 Rev. D	Global Clinical Study Report Template	GEN-0010523	Effective Date: July-2017

The following baseline covariates will be included in the ANCOVA:

- (1) TBUT at baseline. This covariate will be treated as continuous.
- (2) The 4-point severity level of skin rosacea at baseline (0= none; 1 = mild; 2 = moderate; 3 = severe). This covariate will be treated as either a numeric score (continuous) or using orthogonal polynomial contrasts.

7.4.1. Stratified Analysis

To account for the potential loss of IPL treatment effect at one site (hereafter called "A") a stratified analysis will be performed that includes a separate stratum comprising subjects at site A who were treated prior to the corrective action. The strata will be labeled as A1, A2, B, and C for sites A, B, and C, with A1 and A2 the two separate groups of patients at site A before and after the corrective action. Since the treatment is applied over a sequence of four visits, we will conservatively assign to stratum A2 only those patients who received all four of their treatments subsequent to the corrective action. Any patient who received any one of their four scheduled treatments prior to the corrective action will be assigned to stratum A1.

Thus, the following four strata are obtained:

Stratum	Corrective Action	Description
A1	No	Patients from site A with one or more treatment visits prior to the corrective action
A2	Yes	Patients from site A with all 4 treatment visits subsequent to the corrective action
В	No	Patients from site B
C	No	Patients from site C

An ANOVA analysis will be performed for the change in TBUT primary endpoint, with fixed effects for treatment and stratum and a random subject effect.

To examine the effect of the corrective action, we will group the strata into two sets: $\{A1\}$, for the precorrective-action subjects at site A, and $\{A2+B+C\}$ for all post-corrective-action subjects at site A, combined with all subjects at B or C. We will test for significance of the corrective action by creating a 1 degree of freedom contrast for "treatment by corrective action", using treatment (1 df) and the two corrective action sets (1 df), and test whether the contrast is significantly different from 0, using a twosided alpha of 0.15.

QF-1044440 Rev. D	Global Clinical Study Report Template	GEN-0010523	Effective Date: July-2017

- If the contrast is not significant, then the results will be analyzed as planned, pooling across all strata pre- and post- corrective action.
- If the contrast is significant then we will carry out the analyses separately for A1 and for the combined {A2+B+C}.

We will also directly compare outcomes between A1 and A2 by calculating the LSM for the difference between the two, along with the associated 95% CI.

8. Adverse events

8.1. Adverse Events Definitions

In this study, an adverse event is any undesirable clinical occurrence (sign, symptom, illness, or other medical event), that appears or worsens during the clinical study, or requires medical treatment or intervention, whether it is considered to be device related or not. If an adverse event occurs, the first concern will be the safety and welfare of the patient. Appropriate medical intervention will be made.

Any adverse events or complications reported by the subject or observed by the study investigator that occur during or after treatment with the device will be recorded in the medical record or source document and in the eCRF. The study investigator will determine if the adverse event is device related or procedure related. This assessment shall include a description of the adverse event, the onset date, the action taken (drug, surgery, hospitalization, etc.), the outcome (resolved, resolved with residuals, ongoing, etc.), the resolution date (if resolved), the severity, and seriousness.

Each adverse event should be assessed according to the following criteria:

8.1.1. Severity

Each adverse event should be assessed for its severity, or the intensity of an event experienced by the subject.

- **Mild:** Awareness of a sign or symptom that does not interfere with the subject's activity or is transient, resolved without treatment and has no sequelae.
- **Moderate:** May interfere with the subject's usual activity and require additional intervention and/or treatment, and may have additional sequelae.
- **Severe:** Significant discomfort to the subject and/or interferes with the subject's activity. Additional intervention and or treatment are necessary. Additional sequelae occur. Severe is used to describe the intensity of an event experienced by the subject.

8.1.2. Relationship of AE to the device or the procedure

Each adverse event should be assessed for its relationship to the device or procedure as identified as follows:

QF-1044440	Rev. D	Global Clinical Study Report Template	GEN-0010523	Effective Date: July-2017

Device: This category should be restricted to adverse events directly attributable to the study device

Procedure: A procedure is any activity that supports the usage of the device

Use the following categories for assigning the certainty of the relatedness:

Definitely Related: An AE is definitely related if it is obvious, certain or there is little doubt regarding the relationship

Possibly Related: An AE is possibly related if it is capable of being related but relatively unlikely.

Not Related: An AE is not related if it is determined that there is no plausible association.

Unknown: Use this term if there is insufficient information to determine if the AE is related to the device or procedure.

8.1.3. Pre-existing Conditions

A pre-existing condition should not be reported as an adverse event unless there has been a substantial increase in severity or frequency of problems, which has not been attributed to natural history.

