The recommended IPL settings are the numbers to the right of the inequality signs for fluence, pulse duration and pulse delay. For filters, it is recommended to use the values not in parentheses. These values are recommended but can be modified, at the discretion of the investigator. *: Only for subjects in the study arm. For subjects in the control arm, use a filter which blocks all wavelengths. This filter is labeled with a red sticker and the symbol " ∞ ".

Skin type	Fluence (J/cm ²)	Filter (nm) *	Pulse structure	Pulse duration (msec)	Delay (msec)	Chiller
I	≤ 20	560 (or 590)	Triple	≥ 3	≥ 15	On
II	≤ 19	560 (or 590)	Triple	≥ 3.5	≥ 20	On
III	≤ 18	560 (or 590)	Triple	≥ 3	≥ 25	On
IV	≤ 17	590	Triple	≥ 3	≥ 30	On

THIS SPACE INTENTIONALLY LEFT BLANK

Revision: C State: Released ECO No: ca-00000172 Effective Date: 19-Sep-2019

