3.9. Blinding

Every effort will be made to ensure examiners measuring primary outcomes are masked to the treatment allocation. However, due to the nature of the IPL treatment, it is not possible to completely ensure masking of the examiner. The examiner that will assess the outcome measures at the baseline visit and at the follow-up visit will not be the study investigator that will administer the IPL pulses. This will increase the probability that the examiner is masked to the allocation.

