8.1.5. Anticipated Outcome Related Adverse Events

Anticipated adverse events in this study may include:

- Skin reactions including: flare-up, irritation, infection, blistering, pruritis, dryness, temporary skin color changes, burns, prolonged edema or erythema, *Herpes simplex* virus reactivation, post-inflammatory hyperpigmentation (PIH), contact dermatitis, and scarring. If any antibiotic ointment will be required during the study it will be provided by the study investigator at no cost.
- Ocular conditions including: iritis, iris atrophy, uveitis, elevated IOP, photophobia, floaters

Any anticipated AE that occurs at any time during or after the use of the study device must be reported by the study investigator to Lumenis. If the anticipated AE, in the opinion of the Sponsor (Lumenis) or the study investigator, is likely to affect the safety of the subjects or the conduct of the study, the ethical committee will be notified of the effect within 10 working days after Lumenis first

QF-1044440 Rev. D	Global Clinical Study Report Template	GEN-0010523	Effective Date: July-2017

Revision: C State: Released ECO No: ca-00000172 Effective Date: 19-Sep-2019

receives notice of the event. If an adverse event occurs during the course of the study, the study investigator will continue following the subject until the adverse event is resolved, or up to 6 months following the last treatment, whichever comes first.

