5.6.2. Safety Endpoints

- The difference in the incidence of non-ocular adverse events, between subjects in the study arm and subjects in the control arm
- The difference in the incidence of ocular adverse events, between subjects in the study arm and subjects in the control arm
- The difference in the incidence of unanticipated serious adverse events, between subjects in the study arm and subjects in the control arm
- The difference in the level of pain/discomfort during IPL treatment, between subjects in the study arm and subjects in the control arm
- The difference in the level of pain/discomfort during MGX, between subjects in the study arm and subjects in the control arm
- The difference in the change of biomicroscopy immediately before and immediately after IPL treatment, between subjects in the study arm and subjects in the control arm

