5.7. Effectiveness analyses

The primary efficacy outcome measure (TBUT) consist of a pre-treatment measurement (the baseline), a treatment intervention, and a post-treatment measurement (the follow-up). Both eyes will be included in the analysis. Since the two eyes of a subject are not independent, to estimate whether TBUT has improved from the baseline to the follow-up, a linear mixed effects model with random intercept, using the subject identity as the random effect, is the appropriate test. Since there are two eyes per person then there is only one possible covariance structure (i.e. symmetric, with a single correlation between eyes).

The secondary efficacy outcome measures are OSDI and EDS which will be collected at the baseline, and at a follow-up visit. In the case of OSDI, the value is estimated per subject. Hence, a single value will be collected per subject at each of these two visits. In this case a paired t-test is the appropriate statistical test to estimate whether dry eye symptoms have improved, using the change of OSDI from baseline to the follow-up. In the case of EDS, the value is estimated per eye. Hence, two values will be collected per subject at each of these two visits. Since the two eyes of a subject are not independent, to estimate whether EDS has improved from the baseline to the follow-up, a linear mixed effects model with random intercept, using the subject identity as the random effect, is the appropriate test. The level of

statistical significance is $\alpha = 0.05$. Non-parametric tests will be performed if the underlying distributions are not normal.

For all other eye-level analyses, where appropriate, sample means of continuous variables will be analyzed with linear mixed effects model with random intercept (whenever both eyes of a subject are included in the analysis), or two-sample t-tests. Proportions will be analyzed with χ^2 tests.

All statistical tests will be two-sided because potentially the treatment procedure may worsen the outcome. The level of statistical significance (type I error) is $\alpha = 0.05$. Non-parametric tests will be performed if the underlying distribution is not normal.

For descriptive statistics, the N, Mean, Median, Standard deviation, Standard error of the mean, 95% confidence interval, Minimum, and Maximum will be reported for continuous variables; the frequency and proportion for each category will be reported for nominal and categorical variables.

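### Protocol 8.1, 8.1.3 and 8.1.5 conflict on worsened pre-existing conditions, so a causality judgement can keep non-serious dry-eye worsening out of the adverse-event comparison

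*Protocol*

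**What the plan says.** Three parts of Protocol section 8 bear on a condition that is present at entry and gets worse.

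- **8.1** defines an adverse event as any undesirable clinical occurrence "that appears or worsens during the clinical study, or requires medical treatment or intervention, whether it is considered to be device related or not". It requires events reported or observed during or after treatment to be recorded, and it assigns causality: "The study investigator will determine if the adverse event is device related or procedure related".
- **8.1.3** keeps a pre-existing condition out of adverse-event reporting "unless there has been a substantial increase in severity or frequency of problems, which has not been attributed to natural history". It does not say who makes the attribution, does not define natural history or the threshold of a substantial increase, and asks for no log of what is set aside.
- **8.1.5** lists anticipated events, beginning "Skin reactions including: flare-up, irritation, infection, blistering, pruritis, dryness", and obliges the investigator to report any of them. It has no exception for natural history. Worsening of dry eye or of meibomian gland dysfunction (MGD) is not on its list.

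Protocol 8.1.2 separately provides relatedness categories, including not related and unknown.

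The safety endpoints are between-arm comparisons. SAP 5.6.2 includes "The difference in the incidence of ocular adverse events, between subjects in the study arm and subjects in the control arm" and the matching non-ocular endpoint. Protocol 6.2 and SAP 4.2 compare related and unrelated events between arms. SAP 5.6.3 computes ocular incidence as the proportion of subjects with any event. The SAP contains no adverse-event definition that would settle the conflict.

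**The concern.** Under 8.1 an event is recorded first and its cause is judged afterwards. Under 8.1.3 the cause of a worsened pre-existing condition is judged first, and an event attributed to natural history does not enter the adverse-event record. Such an event is, by that attribution, an unrelated event, which Protocol 6.2 and SAP 4.2 say will be compared between arms. The recording rule therefore removes events that a stated safety outcome is meant to count.

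This is not a rare case. Eligibility (Protocol 4.2) requires dry eye disease due to MGD, so every subject has a pre-existing condition in the organ that the ocular endpoint concerns.

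The filter could also act differently in the two arms. Relatedness is judged by the study investigator, and Protocol 3.9 says the outcome examiner "will not be the study investigator that will administer the IPL pulses", so IPL or sham is given by the study investigator. That person can see the allocation: in Protocol 2.5.6, the note to Table 2 says of the sham filter, "This filter is labeled with a red sticker". If the same person makes the natural-history call, knowledge of the arm could influence which events are recorded.

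**Working it through.** **Step 1. Set the rules side by side.**

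| Event | 8.1 | 8.1.3 | 8.1.5 |
|---|---|---|---|
| Substantial dry-eye worsening, attributed to natural history | Adverse event, recorded | Not reported | Not listed |
| Substantial dry-eye worsening, not so attributed | Adverse event, recorded | Reported | Not listed |
| Less than substantial dry-eye worsening | Adverse event, recorded | Not reported | Not listed |
| Skin flare-up in a subject with rosacea, attributed to natural history | Adverse event, recorded | Not reported | Must be reported |

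Rows 1 and 3 are direct contradictions between 8.1 and 8.1.3, with nothing in 8.1.5 to resolve them. Row 4 is a conflict in which two sections require reporting and one bars it. Row 1 is the natural-history problem. Row 3 comes from the undefined threshold and is a separate question.

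**Step 2. Who could apply the filter, and when.** 8.1.3 names no one. At treatment visits and the check-up call, the natural reading is the study investigator (or, for the call, a designee), since 8.1 gives that role the relatedness judgement. At follow-up, Protocol 5.3.2 and 5.3.3 have a different person, the examiner, ask about and record events, and masking of that person is intended. Possible arm-awareness therefore applies mainly before the follow-up visit.

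**Step 3. What the filter does to a between-arm difference.** The plan states no adverse-event rate, so there is no figure to reproduce. All rates and shares below are assumptions chosen to show the range.

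Recorded incidence = true incidence × (1 − share set aside as natural history)

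| True IPL / sham | Share set aside IPL / sham | Recorded IPL | Recorded sham | True → recorded difference (points) |
|---|---|---|---|---|
| 15% / 15% | 40% / 80% | 0.15 × 0.60 = 9% | 0.15 × 0.20 = 3% | 0 → +6 |
| 15% / 15% | 80% / 40% | 0.15 × 0.20 = 3% | 0.15 × 0.60 = 9% | 0 → −6 |
| 20% / 10% | 50% / 50% | 0.20 × 0.50 = 10% | 0.10 × 0.50 = 5% | +10 → +5 |
| 20% / 10% | 75% / 50% | 0.20 × 0.25 = 5% | 0.10 × 0.50 = 5% | +10 → 0 |

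Equal shares shrink a true difference in proportion. Unequal shares can create, reverse or hide one. With the 83 planned completers split evenly (83 / 2 = 41.5 per arm), 6 points is 0.06 × 41.5 ≈ 2.5 subjects.

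**The case against.** The strongest reply is that much of the worsening is seen elsewhere. TBUT, OSDI and EDS are measured at baseline and follow-up and compared by arm. Skin response is graded after every treatment, and longer-term response has its own eCRF section (Protocol 5.2.2). Skin condition is recorded again at follow-up (5.3.3). Biomicroscopy before and after treatment is a safety endpoint in its own right. SAP 5.6.1 tabulates ocular surface staining, IOP and BCVA. Protocol 8.2.1 requires all serious events to be reported whatever their presumed cause. The safety endpoints are only summarised by arm, and no success criterion rests on them. All of this stands. It confines the exposure to the adverse-event record of non-serious worsening. It does not replace that record: TBUT, OSDI and EDS are taken only at baseline and one follow-up, so worsening that resolves in between may be missed by them, and a subject who leaves early may have no follow-up value.

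A reader might infer more than the documents support:

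- *Rosacea flares drop out of the endpoints.* Protocol 8.1.5 requires flare-ups to be reported, so the instructions for them conflict. The share of subjects with rosacea is not stated either.
- *Events set aside cannot be recovered from any later table.* The assessments above retain part of the information.
- *The judgement is made with knowledge of the arm throughout.* This is an inference for treatment visits and the check-up call, and at follow-up the intended arrangement points the other way.
- *The SAP predicts worsening as a harm.* The sentence in SAP 5.7, "All statistical tests will be two-sided because potentially the treatment procedure may worsen the outcome", justifies two-sided tests in the effectiveness section. It does not forecast adverse events.

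**Conclusion.** The contradiction holds on the text alone: a substantial worsening of a pre-existing condition attributed to natural history is an adverse event under Protocol 8.1 and is not reported under 8.1.3, and for flare-ups 8.1.5 also points the other way. The consequence is a permitted under-count of the between-arm incidences, including unrelated events, mainly through non-serious worsening of dry eye or MGD. The under-count may differ by arm, if the treating investigator makes the attribution and is influenced by knowing the allocation.

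Size and direction cannot be determined from the documents. The calculations show only that recorded differences could move by 5 to 10 points either way under plausible-looking but invented inputs, and they are not evidence that this will happen. The primary effectiveness analysis and the success criterion are untouched.

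**What to change.** Reconcile Protocol 8.1, 8.1.3 and 8.1.5. Delete the closing natural-history clause from the 8.1.3 sentence, so that a substantial worsening of a pre-existing condition is recorded as an adverse event, and enter any view that it reflects natural history only in the 8.1.2 relatedness field. Add to SAP 5.6.3 that these events count in the ocular or non-ocular incidence regardless of attribution.

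Leave the threshold of a substantial increase for the sponsor to reconcile with 8.1. Replacing it with any increase at all would go beyond this point: every subject has dry eye, so small fluctuations could then count as ocular adverse events and partly duplicate the effectiveness endpoints.

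The cost is about one sentence in each document, with no new visit, examination or staff. The downside is somewhat higher adverse-event counts in both arms.
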